5.2 Endpoints

5.2.1 Primary Endpoint

The primary endpoint variables will be acceptability of the Cytosponge as demonstrated on the Impact of Event Scale, a visual analog scale, as well as the subject's willingness to undergo repeat Cytosponge administration if it were offered to him/her. Additionally, we will assess the adequacy of the sample, as defined above.

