In the unlikely case of incomplete retrieval or sponge detachment, the sponge will be retrieved with a Roth net at the standard of care endoscopy which will routinely immediately follow the administration of the sponge per the study protocol. Any bleeding noted, either clinically following the sponge administration or due to blood on the sponge itself, will be similarly investigated, and, as necessary, treated during the subsequent endoscopy. Because study inclusion/exclusion criteria are designed to exclude those at highest risk for a bleeding complication, the risk of bleeding in this study should be extremely low.

If a subject fails to swallow the Cytosponge, the subject will be asked to swallow again. Subjects who are willing to try again will be asked to wait 5 minutes before the Cytosponge is presented to them again. Subjects will be able to try up to two times before they are classified as "Cytosponge swallowing failure" and discontinued by the investigator.

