9.3. Visual Analog Scale Administration

Immediately following administration of the initial Cytosponge and retrieval, subjects will be administered a Visual Analog Scale (VAS). The VAS will not be administered during the repeat Cytosponge for subjects requiring a repeat Cytosponge.

This document is electronically controlled

COVB2710467

Version G 01-DEC-2017

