9.9.1. Impact of Event Scale

The impact of event scale will be completed with the subject during the follow-up phone call and measures subjective distress related to administration of the Cytosponge. See **Appendix II:**

Impact of Event Scale.

COVB2710467

Page 29 of 61

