9.9.2. Procedure Preference and Acceptability Questionnaire

The procedure preference and acceptability questionnaire will be completed with the subject during the follow-up phone call. This assessment collects subject preference for the Cytosponge or traditional upper endoscopy as well as willingness to undergo the procedure again.

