9.11. Subject Withdrawal or Discontinuation

Subjects will be considered to have completed the study after completion of the last study visit (followup phone call). Subjects may be withdrawn prior to this for any of the following reasons:

- Death, or
- Lost to follow-up, or
- Withdrawal of consent, or
- Discontinuation by the investigator.

COVB2710467

Documentation must be maintained at the site for any subject withdrawals. Subjects unable to complete Cytosponge administration will be withdrawn from the study (discontinued by investigator). Three attempts at contact using two different methods are required prior to determining the subject is lost to follow-up. Attempts at contact must be with certified letters OR documented telephone contact. If a subject is withdrawn prior to completion of the study, the site should complete the Study Exit e-CRF.

10. Risks and Benefits

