While the operating characteristics of Cytosponge in our patient population are unknown, the numbers for this post-market study were selected for several reasons. Approximately 50% of the patient population at the involved tertiary care centers have dysplastic BE (25% low-grade dysplasia, 25% high-grade dysplasia), so assessment of 275 patients (with an enrollment ratio of at least \geq 50% BE and \geq 25% GERD) should allow an adequate number of subjects with dysplastic disease to assess performance characteristics with reasonable accuracy. Ten percent of patients with chronic GERD symptoms can be expected to harbor BE, leaving us 75 patients with which to assess specificity, as well as to assess acceptability in patients without disease. For the safety perspective, a sample size of 50 will have greater than 90% probability of detecting a rare event that occurs at a rate of 5%. Results of this study will be used to provide more accurate parameters for power of subsequent studies.

All individuals offered the Cytosponge will be included in analyses of acceptability and adequacy of sampling. All individuals with adequate Cytosponge samples and endoscopy (within 48 hours of Cytosponge) will be included to determine the sensitivity for diagnosis of BE from the TFF3 data (95% confidence intervals will be used).

In an effort to understand the sensitivity and specificity of the test, an interim analysis of the data, based on the statistical methodology outlined above, may be performed after approximately half the study subjects have primary outcomes.

To assess safety (fifth secondary objective), the number and percentage of subjects with adverse events related to Cytosponge administration will be summarized by MedDRA system organ class and preferred term overall, and by severity.

COVB2710467

Version G 01-DEC-2017

Page 36 of 61

14. Ethics

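### Acceptability is to be analysed in everyone offered the sponge, but on the plain reading subjects who cannot complete administration are withdrawn before any acceptability measure is taken

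*Protocol*

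**What the plan says.** **Population.** Protocol section 13 states: "All individuals offered the Cytosponge will be included in analyses of acceptability and adequacy of sampling". The SAP repeats the sentence under Sample Adequacy (6.6.1.1.1). SAP 6.1.3 sets a default of available data for all enrolled subjects, but it gives way where something else is specified, so the all-offered statement governs.

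**Withdrawal.** Section 7.2: "Subjects will be able to try up to two times before they are classified as" a swallowing failure and discontinued. Section 9.11: "Subjects unable to complete Cytosponge administration will be withdrawn from the study (discontinued by investigator"). That section treats the follow-up call as study completion and adds: "Subjects may be withdrawn prior to this for any of the following reasons".

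**Timing of the measures.**
- VAS, section 9.3: "Immediately following administration of the initial Cytosponge and retrieval, subjects will be administered a Visual Analog Scale (VAS"). The schedule in 9.1 agrees.
- IES, section 9.9.1: "The impact of event scale will be completed with the subject during the follow-up phone call".
- Preference and willingness, section 9.9.2: "The procedure preference and acceptability questionnaire will be completed with the subject during the follow-up phone call".

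**Endpoint.** Section 5.2.1 names the IES, a VAS and "willingness to undergo repeat Cytosponge administration if it were offered to him/her" as primary acceptability variables.

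**Missing data and disposition.** SAP 6.3 plans no imputation. SAP 6.1.1 tabulates reasons for leaving the study.

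**Adequacy.** Protocol 5.1.1 and SAP 6.6.1.1.1 ask for adequacy after one sampling and also after two where the first is inadequate. The synopses in both documents join the two with an or. The analysis text (Protocol section 13, SAP Sample Adequacy) gives a single proportion, once a second sponge has been allowed.

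**The concern.** The subjects who make the all-offered population different from the completers are those who could not complete administration. If no acceptability measure is collected from them and none is imputed, the acceptability analysis covers completers only, whatever section 13 says.

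This matters most for willingness. Some of the people least likely to accept the device leave before being asked, so the reported proportion would probably be too favourable. No direction can be given for preference, because a subject who failed to swallow could answer either way. The disposition table should let a reader recover the number of failures, but nothing ties that number to the acceptability results.

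Acceptability is a primary endpoint, and section 13 says the results will supply parameters for later studies. A reader who takes the population statement at face value would carry a completers' figure forward as an all-offered one.

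**Working it through.** **1. Do the passages fit together?**
- Stated population: everyone offered the sponge (Protocol 13, SAP Sample Adequacy).
- Exit point for a swallowing failure: during administration (7.2, 9.11).
- Earliest acceptability measure: the VAS, after retrieval (9.1, 9.3). The others come at the day-7 call (9.9.1, 9.9.2), which section 9.11 treats as completion, with withdrawal before it.
- Rule for scoring a subject without data: none (SAP 6.3).

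Every scheduled measure falls after the exit point, so the stated population has no data source for these subjects. That they receive no call is an inference from section 9.11; no sentence says it outright.

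**2. The plan's own swallowing figure.** Protocol 6.2 reports 501 of 504 subjects swallowing the predecessor device, given as 99%. Check: 501/504 = 99.4%. Failures: 3/504 = 0.595%, exact (Clopper-Pearson) 95% CI 0.12% to 1.73%.

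**3. Expected number here.** With up to 275 subjects: 275 × 3/504 = 1.64, or 0.34 to 4.76 over the CI. Chance of at least one failure: 1 − (1 − 3/504)^275 = 0.806.

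**4. Effect on willingness.** The documents give no expected willingness; assume w = 90% among those who answer. Let f be the failure rate, and count every failure as unwilling, which is the extreme case.
- If all completers answer, the result is w(1 − f) = 0.90 × 0.99405 = 89.5%, a shift of w × f = 0.54 points. Over the CI for f the shift is 0.1 to 1.6 points.
- If 10% of completers miss the call (assumed) and are left out, responders are 275 × 0.99405 × 0.90 = 246.0, of whom 0.90 × 246.0 = 221.4 are willing. Then 221.4/(246.0 + 1.6) = 89.4%, a shift of 0.59 points (0.1 to 1.7 over the CI).
- With w from 80% to 95% and missed calls from 0% to 20%, the shift at 3/504 runs from 0.48 to 0.71 points.

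**5. Scale.** The 95% half-width for 90% of 246 responders is 1.96 × √(0.9 × 0.1/246) = 0.037, or 3.7 points. With 10% missed calls, a failure rate of 2% would give a shift of 2.0 points and 5% a shift of 5.0 points, but neither rate appears in the documents.

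**6. Adequacy.** No arithmetic is needed. The objective asks for two proportions and the analysis text reports one.

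**The case against.** The strongest reply has four parts.

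*The endpoints concern people who had the procedure.* The IES measures distress from administration, the VAS follows retrieval, and section 5.2.1 asks about a repeat. A completers' population is therefore a defensible choice. That stands, but it is not the population that section 13 and the SAP state, so one text has to change.

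*Nothing forbids calling a withdrawn subject.* This also stands in part. A reader might infer that the documents state that these subjects are never asked. They do not. Section 9.11 only places withdrawal before the call, and the study exit form and the questionnaire items are not visible. If a call is intended, sections 7.2 and 9.11 need to say so.

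*The effect is negligible.* On the documented rate it is well inside sampling error, and section 13 sets no test or threshold for willingness. A reader might infer a materially biased primary result; the figures do not support that. The one caution is that 3/504 comes from a predecessor device in primary care, while this study uses a refined device at tertiary centres.

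*Inability is not unwillingness.* A reader might infer that swallowing failures should simply be scored as non-acceptors. Section 7.2 re-offers the capsule to those willing to try again, so anyone who failed twice had agreed to a retry, whereas someone who failed once and declined had signalled the opposite. The group is mixed. Scoring all of them as unwilling while leaving out ordinary missed calls is a convention suited only to a sensitivity analysis.

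**Conclusion.** The inconsistency is in the current text of both documents and is minor. On the plain reading of section 9.11, acceptability would be a completers-only result under an all-offered label. The likely error in willingness is favourable, about 0.5 to 0.6 points at 3/504. That size rests on the predecessor-device rate carrying over, an assumed 90% willingness, and every failure being unwilling. Nothing is claimed about the direction for preference.

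The adequacy point is narrower. A reader might infer that subjects without a specimen drop out of adequacy, but the all-offered denominator and the binary definition already imply that they count as not adequate. What is missing is the proportion after the first sponge, which the objective requests and the analysis text does not provide.

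**What to change.** 1. Reconcile Protocol 7.2 and 9.11 with Protocol 13 and the SAP, so that subjects who leave the sponge procedure stay in data collection for the day-7 preference and willingness questions. The attempt rule is not questioned.
2. Report the swallowing-failure proportion, with all offered as denominator and an exact 95% CI, beside the acceptability results and not only in the disposition table. For example, 2/275 would read 0.7% (0.1% to 2.6%).
3. Analyse willingness and preference on the answers given. For willingness, count failures without an answer as not willing in a sensitivity analysis only, stated as an exception to SAP 6.3. Label IES and VAS results as among subjects with scores.
4. If these subjects are not kept in follow-up, the minimum is to restate the acceptability population in Protocol 13 and the SAP as subjects who completed administration, and report the failure proportion with it.
5. Report adequacy after the first sponge and after up to two, each with all offered as denominator and an exact 95% CI.

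Cost: a few SAP sentences, a short protocol amendment with sponsor and IRB approval (Protocol 15.6), and about two phone calls (0 to 5 over the CI of 3/504). The percentages may come out slightly less favourable.

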14.1. Statement(s) of Compliance

This clinical investigation will be conducted in accordance with the US and international standards of Good Clinical Practice (FDA Title 21 and International Conference on Harmonization guidelines), applicable government regulations, Institutional research policies and procedures, ethical principles that have their origin in the Declaration of Helsinki, ICH-GCP, and any regional or national regulations, as appropriate.

The clinical investigation will not begin until all necessary approvals/favorable opinions are obtained from the appropriate IRBs or regulatory authority, as appropriate. Should an IRB or regulatory authority impose any additional requirements, they will be followed. Information regarding the study and study data will be made available via publication on clintrials.gov. Additionally, the results of this study will be submitted for publication in an appropriate journal.

This protocol and any amendments will be submitted to a properly constituted independent IRB, in agreement with local legal prescriptions, for formal approval of the study conduct. The decision of the IRB concerning the conduct of the study will be made in writing to the investigator and a copy of this decision will be provided to the sponsor before commencement of this study. The investigator should provide a list of IRB members and their affiliate to the sponsor.

All subjects for this study will be provided a consent form describing this study and that provides sufficient information for subjects to make an informed decision about their participation in this study. Sample consent forms will be provided by the lead site. These consent forms include a consent for the study as well as a consent for storage of samples for future use. All consent forms will be submitted with the protocol for review and approval by the IRB for the study. The formal consent of a subject, using the IRB-approved consent form, must be obtained before that subject undergoes any study procedure. The consent forms must be signed by the subject or legally acceptable surrogate, and the investigator-designated research professional obtaining the consent.

COVB2710467

Version G 01-DEC-2017

15. Study Administration

15.1. Monitoring

The investigator will permit study-related monitoring, audits, and inspections by the IRB, the sponsor, the lead site, government regulatory bodies, and University compliance and quality assurance groups of all study related documents (e.g. source documents, regulatory documents, data collection instruments, study data etc.). The investigator will ensure the capability for inspections of applicable study-related facilities (e.g. pharmacy, diagnostic laboratory, etc.). Participation as an investigator in this study implies acceptance of potential inspection by government regulatory authorities and applicable University compliance and quality assurance offices.

Participation as an investigator in this study implies acceptance of potential inspection by government regulatory authorities and applicable University compliance and quality assurance offices.

It is the responsibility of the Principal Investigator to oversee the safety of the study at his/her site. This safety monitoring will include careful assessment and appropriate reporting of adverse events as noted above, as well as the construction and implementation of a site data and safety-monitoring plan, if required. Medical monitoring will include a regular assessment of the number and type of serious adverse events.

15.2. Data Management

This study will utilize an electronic database and eCRF or paper CRFs. All data requested on the eCRF are considered required. Data points not collected and/or recorded will be considered deviations unless otherwise specified. The Principal Investigator must ensure the accuracy and completeness of the recorded data and then provide his/her electronic signature on the appropriate eCRFs. The Investigator's electronic signature for specific eCRFs will be documented in compliance with local regulations. Changes to data previously submitted to the sponsor will require a new electronic signature by the Investigator to acknowledge/approve the changes.

Visual and/or computer data review will be performed to identify possible data discrepancies. Manual and/or automatic queries will be created in the Oracle remote data capture (RDC) system and will be issued to the site for appropriate response. The site staff will be responsible for resolving all queries in the database.

The investigator must agree to the inspection of study-related records by the Regulatory Authority/Sponsor representatives, and must allow direct access to source documents to the Regulatory Authority/Sponsor representatives.

This document is electronically controlled

COVB2710467

Version G 01-DEC-2017

15.3. Direct Access to Source Data/Documents

The investigator must agree to the inspection of study-related records by the Regulatory Authority/Sponsor representatives, and must allow direct access to source documents to the Regulatory Authority/Sponsor representatives

15.4. Confidentiality

Information about study subjects will be kept confidential and managed according to the requirements of the Health Insurance Portability and Accountability Act of 1996 (HIPAA). Those regulations require a signed subject authorization informing the subject of the following:

- What protected health information (PHI) will be collected from subjects in this study
- Who will have access to that information and why
- Who will use or disclose that information
- The rights of a research subject to revoke their authorization for use of their PHI.

In the event that a subject revokes authorization to collect or use PHI, the investigator, by regulation, retains the ability to use all information collected prior to the revocation of subject authorization. For subjects that have revoked authorization to collect or use PHI, attempts should be made to obtain permission to collect at least vital status (i.e. the subject is alive) at the end of their scheduled study period.

15.5. Liability

Medtronic maintains appropriate clinical study liability insurance coverage as required under applicable laws and regulations and will comply with applicable local law and custom concerning specific insurance coverage. If required, a clinical study insurance statement/certificate will be provided to the IRB.

15.6. CIP Amendments

No changes to the protocol will be permitted without the written approval from Medtronic and the IRB/EC (at the discretion of the PI and the IRB). It is the responsibility of the sponsor to notify all participating investigators of any revisions to the protocol.

COVB2710467

Version G 01-DEC-2017

Page 39 of 61

15.7. Record Retention

The investigator will maintain the records of the study including all pertinent correspondence, the study protocol with any/all amendments, all correspondence with and approval from the IRB/EC, the clinical trial agreement, the Investigator Agreement, investigational device accountability records, individual subject records, and signed ICFs. Subject files and other source data must be kept for a period of not less than 2 years after the latter of the following two dates: the date on which this investigation is terminated or completed, or the date that the records are no longer required for purposes of supporting a premarket application. Records may need to be maintained by the Principal Investigator for a longer duration if national regulations require or if agreed to in writing with the Sponsor. All data and documents should be made available if requested by relevant authorities.

15.8. Publication and Use of Information

Neither the complete nor any part of the results of the study carried out under this protocol, nor any of the information provided by the sponsor for the purposes of performing the study, will be published or passed on to any third party without the consent of the lead investigator, [name]. Any investigator involved with this study is obligated to provide the lead investigator with complete test results and all data derived from the study. The results from this study will not be used to influence patient management or follow-up.

The Medtronic Publication and Authorship Policy is aligned with the International Committee of Medical Journal Editors (ICMJE) recommendations (www.icmje.org). Medtronic will seek to publish, in appropriate peer-reviewed journals and scientific conferences, results of clinical studies where human subjects are involved, regardless of outcome. While study results are owned by Medtronic, all data on which a publication is based will be made available to all authors as required for their participation in the publication process. Furthermore, data may be published or used by study investigators provided that such publication or use is in accordance with this this protocol, the Medtronic Publication and Authorship Policy, and the Clinical Investigation Agreement. Investigators must submit a copy of all manuscripts and/or abstracts to Medtronic for review and comment 30 days prior to planned submission. Medtronic acknowledges that its right to review and comment shall relate solely to the proprietary, licensing, and/or confidential rights Medtronic may have in such proposed publication, rather than whether such results and/or opinions are favorable to Medtronic.

The publication of sub-studies, post-hoc analyses, regional results, or single-center experiences based on multicenter clinical studies should not precede that of the primary multicenter publication, and should cite the primary publication whenever possible, as required by specific journal and scientific meeting guidelines.

Medtronic involvement in a publication (e.g., funding of the study; sponsor of the study; collection, analysis, and interpretation of data; professional writing assistance) must be disclosed according to journal-specific policies, submission requirements, and prevailing editorial standards, in addition to

Page 40 of 61

COVB2710467

Version G 01-DEC-2017

those specified by the International Committee of Medical Journal Editors. Authors must ensure that an acknowledgement/disclosure statement is included in the body of the manuscript for Medtronic to review for accuracy. All authors must also disclose financial or personal affiliations that could be considered conflicts of interest as per journal/conference requirements.

To enable health care providers, payers, and patients access to the wealth of Medtronic's research, Medtronic will report its scientific data in accordance with the principles outlined in the Guidance Document on Registration and Reporting Results of Company-Sponsored Clinical Trials Under FDAAA 2007 (Title VIII).

